I. Objectives

Our previous research has shown that children exposed to media characters with guns in movies¹ and video games² are more likely to use real guns themselves (e.g., touch them, hold them, pull the trigger). This research tests whether exposure to a gun safety video a week before the study can help counteract dangerous behavior around guns.

II. Background and Rationale

Guns are prominent in movies that target children. An analysis of top selling films found that the depiction of guns in violent scenes in PG-13 films that target youth has increased from the level of G and PG files in 1985 when the rating was introduced, to the level of R films by 2005, to exceed the level of R films since 2012,³ a trend that has continued.⁴ By definition, a PG-13 movie is supposed to have less violence than an R-rated movie. The Motion Picture Association of America says on its website that the violence in a PG-13 movie “does not reach the restricted R category.” Our study shows that it does.

Previous research has shown that when exposed to movie characters that smoke, children are more likely to start smoking themselves⁵; the same is true for characters that drink alcohol⁶. Similarly, research in our lab has shown that children are more to use guns (e.g., handle them, pull the trigger) after exposure to movie characters who use guns.¹ We replicated this study using video games,² and also found that children who had taken a gun safety course were less likely to engage in dangerous behavior around firearms. However, it is difficult to draw causal inferences about the gun safety course because children were not randomly assigned to take or not take a gun safety course.

The present research will aim to reduce dangerous behavior around firearms by first exposing participants to a gun safety video recorded by The Ohio State University Chief of Police. The control video is about car safety. Children will see the videos about a week before they come into the lab. We predict that children will be less likely to engage in dangerous behavior around real firearms if they saw the gun safety video than if they saw the car safety video, even if they see a movie with guns in the lab.

III. Procedures

A. Research Designs, Samples, Measures, and Procedures

Design

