The experiment will test the effects of the mere presence of guns in movies on dangerous behavior with guns in children. Participants will be children 8-12 years old. Children will be tested in pairs. Each child will bring a sibling, relative, or friend to the study. Participants and partners will each receive a \$30 gift card (\$5 for watching the safety video at home and \$25 for doing the lab study). The behavioral measure will be whether or not children handle a real (but non-firing) gun and whether they pull the trigger, including at themselves or their partners.

The design will be a 2 (movie clip-guns present vs. movie clip-guns absent) x 2 (gun safety video vs. seatbelt safety video) between-subjects design. Participants will be randomly assigned to conditions, but both children in the dyad will watch the same safety video.

We predict a main effect for type of movie (i.e., children who see movie characters use guns will be more likely to use real guns themselves than will children who do not see movie characters use guns), a main effect for type of safety video (i.e., children who see the gun safety video will be less likely to use real guns themselves than will children who see the car safety video), and an interaction between type of movie and type of safety video (i.e., the movie with guns will have a weaker effect on children who see a gun safety video than on children who see a car safety video).

Procedure

Participants will be told that the study is about what children like to do for fun, such as watch videos and play with toys and games. Participants who agree to participate in the study will be sent consent (adult) and assent (child) forms electronically, along with a pretest for both adult and child to complete, should they consent and assent to participating in the study. These pretests were used in our previous research.^{1,2} After informed consent is obtained, the participants will be sent the safety video for the condition to which they are assigned (i.e., gun vs. car safety video), a short questionnaire about the video, and a \$5 electronic gift card. Approximately one week after being sent the video, the participants will come to the lab for the study.

Experimenters and research assistants will be wearing masks at all times and will be fully vaccinated against COVID-19. The lab space will be sanitized between sessions to ensure participant safety.

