NCT05257837

**Follow-up Gun Study:
Can Safety Videos Mitigate Interest in Guns in Children?**

Statistical Analysis Plan

Uploaded 4/5/2023

Statistical Analysis Plan

Data Collection

Data will be collected in two ways. First, some data are entered directly into Qualtrics surveys by parents/guardians and participants in the home and in the lab. In the home, parental consent, child assent, and questionnaire data (i.e., gender, age, trait aggressiveness, age-inappropriate movie consumption, interest in guns, whether participants had taken a firearm safety course or watched a firearm safety video, and whether participants had a firearm at home) will be collected directly online via Qualtrics. In the laboratory, participants will also provide questionnaire data (i.e., attitudes towards guns, whether they have fired a gun before, safety video evaluation, movie evaluation) on iPads via Qualtrics. Second, participants' reporting and handling of the handguns (i.e., whether the child found the gun, told an adult about the gun, touched a gun, time spent handling a gun, total trigger pulls, trigger pulls while pointing the gun at the partner/self) will be recorded via video using a hidden camera. The videos will be coded by trained research assistants who are blind to experimental conditions and study hypotheses.

Data Cleaning

Data cleaning will be done in Excel, SAS, and R. Once the data have been cleaned, the variables will each be examined via summary statistics. Internal reliability of the survey batteries will be assessed via Cronbach's alpha and McDonald's omega. If necessary, variables will be transformed to conform to the assumptions of the statistical tests. Potential outliers will be identified. As in our previous research¹, an outlier is defined as a score at least five standard deviations above or below the mean.

Data Analysis Software

Negative binomial regression models (to determine the predictors of total trigger pulls, trigger pulls while pointing the gun at the partner/self, and time spent handling a gun) will be run using Stata statistical software version 17 (StataCorp). All other analyses were performed using SPSS version 28 and R statistical software version 4.2.1 (R Project for Statistical Computing).

Data Analyses

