Preliminary bivariate and chi-squared tests will be run on the outcome variables. As in our prior studies^{1,2}, two sets of models will be run: (1) a reduced model that includes experimental conditions and gender, and (2) a full model that includes experimental conditions and covariates.

Incidence rate ratios (IRRs) with *SEs*, *z*-tests, and the corresponding 2-tailed *p*-values will be reported for both types of models. Nonsignificant variables (at the 2-tailed .05 significance level) will be excluded from models.

¹ <https://jamanetwork.com/journals/jamanetworkopen/fullarticle/2734799>

² <https://jamanetwork.com/journals/jamapediatrics/fullarticle/2654597>

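### The SAP drops every nonsignificant variable from its models, without exempting the randomised movie and video factors or naming the full model's covariates

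*SAP*

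**What the plan says.** The SAP's Data Analyses section announces two sets of models: "1) a reduced model that includes experimental conditions and gender, and (2) a full model that includes experimental conditions and covariates". IRRs with SEs, z-tests and two-tailed p-values "will be reported for both types of models". The next sentence is the selection rule: "Nonsignificant variables (at the 2-tailed .05 significance level) will be excluded from models".

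The Data Analysis Software section applies negative binomial regression to three outcomes, "to determine the predictors of total trigger pulls, trigger pulls while pointing the gun at the partner/self, and time spent handling a gun".

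No list of full-model covariates appears. The Data Collection section lists what is gathered. The home items are gender, age, firearm at home and "trait aggressiveness, age-inappropriate movie consumption, interest in guns, whether participants had taken a firearm safety course" (or had watched a firearm safety video). The lab items are "attitudes towards guns, whether they have fired a gun before, safety video evaluation, movie evaluation". None of these is assigned to a model. The protocol's Data Analysis section (III.D) names negative binomial regression only, with no covariates and no selection rule.

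**The concern.** The model definitions put the experimental conditions in both models, while the exclusion rule removes any variable that is not significant. When a condition has p above .05, the two statements conflict. The SAP does not say which governs, or whether IRRs are taken before or after exclusion. The safety video is the trial's central question, so a null video result might be published with no estimate at all.

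If the rule is meant only for gender and the covariates, it is still selection by p-value. The adjustment set then depends on the data, can differ among the three outcomes, and starts from an unnamed pool. Nothing keeps out lab items, which are collected about a week after the safety video was sent. The protocol's Procedure places the gun-attitude measure after the play period. Conversely, prior gun safety training would be dropped whenever its p-value exceeded .05, although the protocol's Background reports that "children who had taken a gun safety course were less likely to engage in dangerous behavior around firearms".

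**Working it through.** **1. The text.** Neither document contains an exemption for the conditions or a covariate list for the full model. The reference to prior studies points to outside papers and supplies no list here. The home items are pre-exposure: the protocol's Procedure sends the consent and assent forms "along with a pretest for both adult and child to complete", and the video follows consent.

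**2. Inputs.** From the documents: N = 2 × 104 = 208, which reproduces the protocol's figure; 104 per video level if allocation is equal; two-sided .05. The documents give no power, effect size, mean or dispersion. Assumed: mean 3, variance μ + μ²/k with k from 0.3 to 1.0, movie IRR 2, independent children.

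**3. Literal reading, general result.** A term is kept only if |z| > 1.96. With expected z equal to m, the retained log-IRR divided by the true one is approximately 1 + φ(1.96 − m)/(m × power).
- 50% power: m = 1.96, 1 + 0.399/(1.96 × 0.50) = 1.41
- 80% power: m = 2.80, 1 + 0.280/(2.80 × 0.80) = 1.12
- 95% power: m = 3.60, 1 + 0.103/(3.60 × 0.95) = 1.03

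**4. Literal reading, this trial.** Simulation of backward elimination over movie, video and gender (no interaction fitted, since the SAP names none), 2,000 trials per cell, k = 0.3, 0.5 and 1.0:

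| True video IRR | Video removed | Mean retained IRR |
|---|---|---|
| 1.0 | 94–95% | – |
| 0.7 | 42–71% | 0.50–0.63 |
| 0.5 | 1–24% | 0.44–0.50 |
| 0.4 | 0–7% | 0.38–0.40 |

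Hand check for IRR 0.7, with SE = √[2(1/3 + 1/k)/104]:
- k = 0.3: SE 0.266, z = 0.357/0.266 = 1.34, power 27%, so 73% removed (simulated 71%).
- k = 1.0: SE 0.160, z = 2.23, power 61%, so 39% removed (simulated 42%).

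**5. The interaction.** The protocol's Design section predicts a movie-by-video interaction. If a main effect has 80% power (z = 2.80), an interaction of the same size on the log scale has twice the SE, so z = 1.40 and power is about 29%. If fitted, it would be dropped about 71% of the time.

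**6. Covariates-only reading.** A fixed model (both conditions, interaction, seven home items) was compared with elimination of covariates only on the same simulated data, with 1,600 trials per cell (2,400 for a null video) and k = 0.3 and 1.0.
- The mean video log-IRR moves by at most 0.003.
- With all seven items null, or two at 50% power, there is no material loss.
- With all seven at 50% power and video IRR 0.5, the SD of the video log-IRR rises from 0.303 to 0.323 (k 0.3) and from 0.176 to 0.184 (k 1.0). The mean reported SE stays at 0.272 versus 0.273, and at 0.165 in both.
- In the same seven-covariate case with a null video, type I error goes from 8.0% to 9.7% (k 0.3) and from 5.5% to 6.5% (k 1.0).
- The video verdict at .05 differs from the fixed model in 5–8% of trials when video power is about 28–75%, in 2–4% when the video is null, and in under 1% at 98% power.
- With seven null, independent candidates, the chance of keeping at least one is 1 − 0.95⁷ = 30% per outcome.

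**The case against.** The most coherent reading is that the conditions stay, because the models are defined by them, and that the rule trims the rest. On that reading the estimate is unbiased and the 4–7% loss needs seven independent covariates at 50% power each, which is an extreme case. This stands. The large literal-reading figures also need reporting after exclusion, which the SAP does not state.

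The exaggeration is not created by the model. In a given trial the retained estimate hardly changes, and significant IRRs would be just as exaggerated without the rule. This also stands. The harm is that the nonsignificant estimates go unreported.

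The 5–8% disagreement needs a benchmark. In a re-simulation of 400 trials per cell, the reduced and full models, both fixed, disagreed on the video in 9–19% of trials at moderate power. Fixing the covariates therefore leaves a larger ambiguity, because the SAP does not say which model is primary.

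Children are tested in pairs that share a safety video. At an assumed within-pair correlation of 0.2–0.5 with unadjusted SEs, a null video would be kept about 7–11% of the time rather than 5–6%. The simulated ranges are therefore narrower than the design supports.

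Finally, having fired a gun before is a history item, and excluding it because it was asked in the lab is a conservative choice.

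These points reduce the size of the problem. They do not supply the missing exemption or the missing list.

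**Conclusion.** The concern holds and should be fixed. That conclusion rests on the text and needs none of the assumed values. Followed literally, the rule contradicts the model definitions, and a null video factor would lose its IRR in roughly 19 of 20 trials if reporting follows exclusion. At low to moderate power the surviving IRRs would also lie too far from 1; at high power that bias is immaterial. Read as covariates-only, which may be the intent, bias is nil and the precision cost is nil to small. What remains is a final model not fixed before the data are seen, with SEs that ignore the selection, and a verdict that can turn on it when video power is moderate. Moderate power cannot be ruled out, because the sample size comes from doubling an earlier study and no power is stated.

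**What to change.** Delete the exclusion sentence and state in the SAP:
- Movie condition and safety video condition stay in both models whatever their p-values, and gender stays in the reduced model.
- The full model keeps gender, age, trait aggressiveness, exposure to age-inappropriate films, interest in guns, earlier firearm safety course or video, and a firearm in the home. The sponsor may shorten this list if it is fixed before analysis.
- Items collected in the lab are not covariates.
- The movie-by-video term is fitted and reported whatever its p-value. Conditions are coded −1/+1 (IRR = exp(2b)), or average marginal effects are used, so that each main effect is averaged over the other factor.
- All IRRs carry 95% confidence intervals.

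The cost is SAP wording, seven covariate degrees of freedom and one for the interaction. All the items are already collected, and the sample size does not change. If all seven covariates are null, keeping them raises the SD of the video log-IRR by 2–4%.

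The coding must be stated. Under 0/1 coding with the interaction, the main-effect SE becomes √[2(1/3 + 1/k)/52] instead of √[2(1/3 + 1/k)/104], a factor of √2. For a video IRR of 0.5 at mean 3, power then falls from 58% to 33% (k 0.2) and from 99% to 86% (k 1.0).
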